All specimens were processed by the laboratory in a Class 2 laminar flow biological safety cabinet. Specimens were inoculated onto the following microbiological media: blood agar (trypticase soy agar with 5% sheep blood), chocolate agar, Brucella agar (with blood, hemin, and vitamin K), and brainheart infusion broth. All media, with the exception of the Brucella agar, were incubated at 37 °C with 5% CO₂ for 21 days. Brucella agar plates were incubated anaerobically at 37 °C for 21 days. Plates were sealed in a manner that allows sterile aeration without desiccation. Media were examined daily for growth visually but were only opened if growth was noted.

The cultures results were reported in a semiquantitative manner as the Specimen Cutibacterium Value (SpCuV) across a range of 0 (no growth) to 4 (4+ positive growth on agar plates).

SAP

An a priori sample size calculation was performed using previous data regarding growth of Cutibacterium from the skin of shoulder arthroplasty patients. Based on pilot data combined with previous published data, we estimated the incidence of positive Cutibacterium cultures on the skin surface of male patients to be 77%. We determined the sample size of 50 was necessary to detect a reduction of 50% between the two groups with 1:1 allocation ratio, a power of 0.80, and an alpha of 0.05. Given that the intervention and outcome were only separated by 1 day, we anticipated a 0% dropout rate. Baseline demographics were compared between groups using a t test for continuous variables and a chi-square test for categorical variables. The two groups were compared with regards to the percent positivity of the skin surface and incised dermal edge as well as the bacterial load at each site using a chi-square test.

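### Bacterial load is an ordered 0–4 grade, but the SAP compares it with an unspecified chi-square test that, on its natural reading, ignores the order and gives no direction

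*Combined protocol and SAP*

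**What the plan says.** The last paragraph of the Study Protocol section reports cultures as a semiquantitative value, the SpCuV, "across a range of 0 (no growth) to 4 (4+ positive growth on agar plates". It is the only graded culture measure in the document.

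The final sentence of the SAP covers both kinds of outcome: "The two groups were compared with regards to the percent positivity of the skin surface and incised dermal edge", and then "as well as the bacterial load at each site using a chi-square test". The sentence before it deals with baseline data, "using a t test for continuous variables and a chi-square test for categorical variables".

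For load, the SAP states no table layout, degrees of freedom, trend scores, cut-point or effect measure. The sample size is set on skin-surface positivity alone: a 77% rate, with 50 patients needed "to detect a reduction of 50% between the two groups".

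**The concern.** The trial asks which wash leaves less *Cutibacterium* on the shoulder. For load, that is a question about direction on an ordered scale. A Pearson chi-square on a 2×5 table (up to 4 df) tests whether the two grade distributions differ in any way at all. It treats grades 0 and 4 as no further apart than grades 0 and 1.

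Two errors of interpretation follow:

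- A significant result may be read as a reduction in load when the arms differ only in the pattern of grades.
- A steady shift toward lower grades may go undetected because the test spreads its power over four degrees of freedom.

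With no load estimate planned, nothing beside the p-value shows which wash did better or by how much.

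The unordered reading is the natural one. The chi-square label has just been used for categorical baseline variables, and the same sentence applies it to positivity. Load is listed in addition to positivity, so it is unlikely to mean the 0 versus above-0 split again. A chi-square test for trend would use the order, but the SAP does not name one.

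**Working it through.** **Inputs.** From the document: grades 0 to 4; skin positivity 77%; 50% reduction, read as relative (77% × 0.5 = 38.5%); N = 50, 1:1; power 0.80; alpha 0.05, taken as two-sided. Assumed: whole-number grades (five levels), load means the SpCuV, and all grade mixes, since the document gives none.

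**1. The plan's own figure.** For two proportions without continuity correction,

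n per arm = [1.96·√(2·p̄·q̄) + 0.8416·√(p₁q₁ + p₂q₂)]² / (p₁ − p₂)², with p̄ = 0.5775.

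- First term: 1.96 × √0.4880 = 1.369.
- Second term: 0.8416 × √(0.1771 + 0.2368) = 0.541.
- n = 1.9106² / 0.385² = 3.650 / 0.1482 = 24.6, so 25 per arm and 50 in total (power 0.806).

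The stated N reproduces. It concerns positivity only.

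**2. The Pearson test ignores order.** With equal arms, X² = Σ(a − b)²/(a + b) over the grades. For 3/4/5/6/7 against 10/6/4/3/2:

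49/13 + 4/10 + 1/9 + 9/9 + 25/9 = 8.06, 4 df, p = 0.089.

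Reordering the columns leaves this unchanged. The Wilcoxon p-value is 0.005 in the true order and 0.36 after one such reordering. This property needs no assumption about grade mixes.

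**3. Significant with equal load.** Counts in grades 0–4: 5/5/5/5/5 against 5/0/10/10/0.

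- Both arms are 20/25 = 80% positive; both mean grades are 50/25 = 2.0.
- X² = 0 + 25/5 + 25/15 + 25/15 + 25/5 = 13.33, 4 df, p = 0.010 (permutation 0.008).
- The Mann–Whitney probability is 0.50 and Wilcoxon p = 1.00.

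**4. Not significant with lower load.** 5/5/5/5/5 against 9/7/5/3/1.

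- Mean grades are 50/25 = 2.0 and 30/25 = 1.2.
- X² = 16/14 + 4/12 + 0 + 4/8 + 16/6 = 4.64, 4 df, p = 0.33.
- Mann–Whitney probability = (9×0.8 + 7×0.6 + 5×0.4 + 3×0.2 + 1×0)/25 + 0.5×0.2 = 0.66.
- U departs from its null mean by 625 × 0.16 = 100. Its tie-corrected variance is (625/12) × (51 − 6150/2450) = 2525.5, so z = 100/50.25 = 1.99 and p = 0.047 (permutation 0.048).

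**5. Rejection rates.** 25 per arm, two-sided 0.05, 100,000 simulated trials per scenario (Monte Carlo SE at most 0.0016). Three assumed base mixes for grades 0–4: (.23, .1925×4), (.23, .33, .22, .14, .08) and (.23, .08, .14, .22, .33). The common odds ratio that moves positivity from 77% to 38.5% is (.615/.385)/(.23/.77) = 5.35.

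| Scenario | Pearson | Wilcoxon |
|---|---|---|
| Proportional-odds shift, 77% to 38.5% | 0.67–0.71 | 0.88–0.89 |
| 77% to 38.5%, grade mix among positives unchanged | 0.59 | 0.71 |
| Positivity fixed at 77%, grades fall among positives only (odds ratio 5.35) | 0.42–0.57 | 0.33–0.44 |
| Positivity falls, grades among positives rise: (.23, .1925×4) vs (.615, 0, 0, .085, .30) | 0.96 | 0.26 |
| Same positivity, mean grade and Mann–Whitney probability, different pattern: (.23, .1925×4) vs (.23, .035, .35, .35, .035) | 0.59 | 0.05 |

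A linear trend test with scores 0–4 has power 0.85–0.89 in the first row and 0.60–0.71 in the second. In the second row the 2×2 positivity test, at 0.84, beats all three.

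With no difference between arms, Pearson rejects in 0.044–0.048 of trials. With arms of 20 and 30, which simple randomization allows, Wilcoxon's gain is 17–25 points in the first scenario and 11–13 in the second.

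**The case against.** The SAP says only that a chi-square test is used. A trend test belongs to that family, and a dichotomised grade is possible. The firm finding is therefore under-specification; the power loss arises only if the unordered version is used. If a trend test was meant, the gap to Wilcoxon is about 0–11 points. The protocol gives only the two ends of the scale, so five levels is an inference, as is the link from bacterial load to the SpCuV.

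The power comparison also depends on the alternative. The largest gain comes from a proportional-odds shift, which suits Wilcoxon, while Pearson leads by 9–13 points when only grades among positives fall. The equal-load table is constructed: it shows what can happen, not what is likely. All the tabulated rates use the skin rate, and no dermal rate is given. Load is not the outcome the trial was sized on.

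Most of this stands as a limit on the size of the effect. It does not remove the point. The ordering argument holds for any number of levels above two. Where Pearson reaches 0.96 against opposing shifts, the result does not indicate lower load. Reading direction from the grades presupposes a grade table, to which the SAP does not commit. For the dermal edge, two assumed mixes with lower positivity also favoured Wilcoxon under a proportional-odds shift (0.40–0.52 against 0.18–0.28). That shows the direction only, since the document supplies no dermal figures.

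**Conclusion.** The concern holds. As written, the load comparison does not commit to using the order of the scale and has no directional estimate, so a significant result need not mean that either wash lowers load. That conclusion rests on the text and on the order-invariance of the Pearson test.

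The power cost is conditional on the unordered reading and on assumed grade mixes. For shifts that carry the planned halving of skin positivity, Wilcoxon gains 18–21 points under proportional odds and 12 points with the mix among positives unchanged. The ranking reverses when the fall in grade is confined to the positives.

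The problem is limited to load. False positives are not inflated, chi-square is suitable for 2×2 positivity, and the sample size of 50 stands. It should be fixed, but it does not threaten the comparison for which the trial was sized.

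**What to change.** In the SAP:

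- State that bacterial load is the SpCuV grade, and list its possible values.
- Compare the arms on it at each site with a tie-corrected or permutation Wilcoxon–Mann–Whitney test.
- Report the Mann–Whitney probability, or a proportional-odds odds ratio, with a 95% CI.
- Tabulate every grade by arm and site.
- Keep the chi-square test for the 2×2 positivity comparison.
- If a chi-square test for trend was intended, name it and give its scores.

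This costs one or two sentences of wording and needs no new data or patients. The downside is less sensitivity to non-directional differences in pattern and to a fall in grade confined to the positives. The grade table covers both descriptively.
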